### 7.2 DATA DERIVATIONS AND DEFINITIONS

## **Baseline Definition**

Baseline measurement is defined as the last pre-treatment measurement obtained prior to the initial administration of BVD-523.

## **Change from Baseline**

The change from baseline will be calculated by subtracting the baseline values from the individual post-procedure values. If either the baseline or post-procedure value is missing, the change from baseline is set to missing as well.

Study days on or after the initial dose of BVD-523 will be computed as Study Day = Date – Study Drug Start Date + 1. For pre-dosing dates, Study Day = Date – Study Drug Start Date.

Age will be calculated from the date of birth to informed consent visit date. Note, that if multiple dates occur for the screening visit, the convention as described at the end of Section 7.3.1 will be used.

Treatment-emergent events will be considered as any event occurring after the first dose of study drug and prior to a subject's termination, withdrawal, or completion of the study.

The following will define prior medication use versus concomitant medication use:

- Prior use ended before the first day of study drug
- Concomitant use is on or after the first day of study drug (initiation date, stop date).

#### 7.3 MISSING DATA

#### 7.3.1 Date Values

In cases of incomplete dates (e.g., pertaining to AE, concomitant medication, medical history, etc.), the missing component(s) will be assumed as the most conservative value(s) possible. For example, if the start date has a missing day value, the first day of the month will be imputed for study day computations (i.e., treatment-emergent status, etc.). If day is missing for an end date, the last day of the month will be imputed. Similar logic will be assumed for missing month and year components.

Date imputation will only be used for computational purposes e.g., treatment-emergent status, etc. Actual data values as they appear in the original CRFs will be shown in the data listings.

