## 5.2.6 Treatment Discontinuation Visit

At the time of study drug discontinuation, the Treatment Discontinuation Visit should be completed for all patients as soon as possible after the last dose of study drug, and every effort should be made to perform the procedures required.

Patients will return to the clinic or will be contacted for a safety follow-up assessment 30 days  $\pm$  3 days after the last dose of study drug was taken; or earlier if subsequent therapy for AML or MDS is initiated prior to 30 days  $\pm$  3 days. Only information about AEs and SAEs will be collected at this visit.

The following procedures will be performed at Treatment Discontinuation Visit:

- Review medical history
- Record medications including start/stop dates, indication, dose and frequency.
- Perform and record physical examination.
- Assess and performance status (ECOG).
- Record vital signs. Measure body temperature, systolic / diastolic BP and pulse rate.
- Perform and record ophthalmology examination.
- Perform urine pregnancy test for female patients who are not postmenopausal or surgically sterile. If urine test is positive, collect blood for a serum pregnancy test.
- Assess and record disease status.
- Bone marrow aspirate and/or biopsy. Peripheral, Geimsa and Iron stained slides will be collected with each bone marrow aspirate or biopsy. Collection not needed if termination is due to progression.
- Bone marrow cytogenetics in accordance with local pathology requirements. (Cytogenetics would preferably include at least 20 clones). Collection not needed if termination is due to progression. Collect blood samples for blood chemistries, hematology and creatinine clearance.

- Collect urine samples for urinalysis.
- Assess and record AEs.
- Obtain all unused study drug from patient.
- Assess study drug compliance by reviewing pill count.

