### **Treatment Emergent Adverse Event**

A treatment emergent adverse event (TEAE) is any AE temporally associated with the use of BVD-523 (from BVD-523 initiation until 30 calendar days after the last administration of BVD-523), whether or not considered related to the study drug. If the onset of an AE is missing and the AE resolution date is either after the initial BVD-523 dose date or missing, then the AE will be considered treatment emergent.

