## **AE Summaries**

A subject who reported multiple AEs that map to a common PT or SOC is counted only once for that PT or SOC at the highest severity reported and at the greatest relationship to study drug. The number and percentage of subjects who experienced at least one AE as well as subjects who experienced at least one TEAE will be tabulated by SOC and PT with respect to dose level treatment group for each study part. The same tabulation will also be applied to any treatment emergent SAEs and any TEAEs leading to premature discontinuation from the study as well as to any DLTs.

Page 28

<sup>1 All toxicities will be considered related to BVD-523 if they cannot be definitively explained by underlying disease, intercurrent illness or concomitant medications.

The number and percentage of subjects who experience at least one TEAE will also be tabulated by SOC and PT within each dose level treatment group with respect to relationship to study drug (unrelated and at least possibly related [combining events classified as either possibly related or related]) and severity (Grade 1 to Grade 5 and ≥Grade 3). The tabulation by relationship

(unrelated and at least possibly related) will also be applied to any treatment emergent SAEs (TESAEs).

Subject listings will also be provided for all AEs, all SAEs, all AEs leading to early discontinuation from the study, all AEs leading to study drug interruptions and length of interruptions.

Bar graphs of AEs in CTCAE Term will be displayed in decreasing order of incidence from most common to least common. Each bar in the plot will represent an AE in CTCAE Term. Severity of AE (grades) will be embedded in each bar using the percentages of subjects in each AE grade. These plots will be provided for all AEs, TEAEs, treatment-emergent SAEs, and AEs leading to premature discontinuation from the study.

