#### 16.2.7 Adverse Event Listings

- Part II Listing 16.2.7.1 Listing of Relationship of WHO Drug ATC Classification and Preferred Term with Verbatim
- Part II Listing 16.2.7.2 Listing of RP2D from Part I
- Part II Listing 16.2.7.3.1 Listing of Treatment Emergent Adverse Events
- Part II Listing 16.2.7.3.2 Listing of Treatment Emergent Adverse Events Leading to Premature Discontinuation from the Study
- Part II Listing 16.2.7.3.3 Listing of Treatment Emergent Adverse Events Leading to Study Drug Delays/Interruptions and Length of Delays/Interruptions
- Part II Listing 16.2.7.3.4 Listing of Treatment Emergent Adverse Events Leading to Study Drug Reductions and Length of Reductions

- Part II Listing 16.2.7.3.5 Listing of Treatment Emergent Adverse Events Related to BVD-523
- Part II Listing 16.2.7.3.6 Listing of Treatment Emergent Adverse Events by Severity
- Part II Listing 16.2.7.4 Listing of Treatment Emergent Serious Adverse Events
- Part II Listing 16.2.7.5 Listing of Deaths

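### First-of-month imputation turns some early on-treatment AEs into pre-treatment events, and the SAP defines the treatment-emergent period in two different ways

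*SAP*

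**What the plan says.** SAP 7.3.1 gives a principle for incomplete dates: "the missing component(s) will be assumed as the most conservative value(s) possible". Its worked example is the only operating rule: "if the start date has a missing day value, the first day of the month will be imputed for study day computations". The section names treatment-emergent status as a use of the imputed date and extends the same logic to missing months and years. SAP 7.3.2 likewise uses imputed dates to sort AEs into pre-treatment, during treatment and post-treatment.

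The treatment-emergent period is defined twice.

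- SAP 7.2 closes the period when the patient terminates, withdraws from or completes the study. Its sentence begins "Treatment-emergent events will be considered as any event occurring after the first dose of study drug and prior to a".
- SAP 10.2, under Treatment Emergent Adverse Event: "from BVD-523 initiation until 30 calendar days after the last administration of BVD-523".

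SAP 10.2 adds a fallback. "If the onset of an AE is missing and the AE resolution date is either after the initial BVD-523 dose date or missing", the event counts as treatment emergent. It does not say whether a partly known onset date is missing for this purpose.

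**The concern.** For a start date, the first of the month is cautious about duration, because it makes the event as long as possible. It is not cautious about the treatment-emergent flag when the known month is the month of first dose, because it moves the onset to before treatment. The example then defeats the principle it is meant to illustrate.

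The flag decides which events enter nearly all the Part II AE tables and figures in SAP 14.3 and the AE listings in 14.5. The first DLT criterion also requires a treatment-emergent event, so the Part 2 DLT tabulation could be touched. The error removes early on-treatment events from the safety summaries of a trial whose first primary objective is safety.

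With two definitions of the period and no statement of which governs, two programmers could also flag the same event differently near the end of follow-up.

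**Working it through.** The plan gives no figure on this point, so the rule was applied directly.

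**Worked example.** First dose 10 March, true onset 18 March (Study Day 9), recorded as March with the day missing. The imputed onset is 1 March. By the SAP 7.2 formula for pre-dosing dates, Study Day = 1 − 10 = −9. The event is pre-treatment under both SAP definitions. If the true onset is 2 April, the imputed date is 1 April (Study Day 23) and the event keeps its flag. At the start of the window, the day-missing error is confined to the month of first dose.

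**How often.** Inputs: the SAP 7.3.1 rule; each of the 365 first-dose dates in a non-leap year taken once; true onset uniform over Study Days 1 to W. The last two are assumptions. An event is misclassified when onset falls in the month of first dose and first dose is not on the 1st.

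For W = 21, a first dose on day x of an n-day month gives min(21, n − x + 1) misclassified onset days. Summing over x = 2 to n gives 420 for a 31-day month, 399 for a 30-day month and 357 for February:

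7 × 420 + 4 × 399 + 357 = 4,893, out of 365 × 21 = 7,665, which is 63.8%.

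Once W covers a whole month, the count stops growing. It is n(n − 1)/2 per month:

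7 × 465 + 4 × 435 + 378 = 5,373.

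| Onset window | Day missing | Day and month missing (1 January imputed) |
|---|---|---|
| Days 1–21 | 4,893/7,665 = 63.8% | 7,434/7,665 = 97.0% |
| Days 1–42 | 5,373/15,330 = 35.0% | 14,427/15,330 = 94.1% |
| Days 1–63 | 5,373/22,995 = 23.4% | – |
| Days 1–180 | 5,373/65,700 = 8.2% | 49,410/65,700 = 75.2% |

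**Share of all AEs.** The documents give no rate of partial dates. If 1% to 10% of Cycle 1 AEs lack the day (assumption), the share losing the flag is 0.638 × 1% = 0.6% to 0.638 × 10% = 6.4%.

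**Other direction.** At the far end the rule can pull a late event in. With a last dose on 10 March, the 30 days end on 9 April. An onset on 20 April recorded as April is imputed to 1 April and counted. The error is therefore not strictly one-way.

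**The SAP 10.2 fallback.** If it covers only wholly missing onsets, an unresolved AE with no onset date is treatment emergent, while one known to have begun in the month of first dose is not. If it also covers partial dates, it contradicts SAP 7.3.1. Either reading needs a correction.

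**The two windows.** Protocol 5.2.6 says "Patients will return to the clinic or will be contacted for a safety follow-up assessment 30 days" after the last dose, with a 3-day tolerance.

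- If completion is dated at that contact (day 27 to 33), the SAP 7.2 end point differs from day 30 by at most 3 days.
- If termination is dated at the last dose, the difference is up to 30 days.
- Either gap is shorter if new anticancer therapy starts, because AE reporting then ends.

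The start points differ too: SAP 7.2 requires an event after the first dose, while SAP 10.2 counts from initiation.

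**The case against.** The best counter-argument is that the practical effect is small.

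- The percentages apply only to partial dates. AEs are assessed weekly in Cycles 1 and 2, the eCRF has online checks and queries, and SAE reports ask for onset date and time. A Cycle 1 onset with the month unknown is unlikely.
- DLTs are reviewed as the study runs, and nothing says that they are derived from imputed dates.
- The trial is single-arm with descriptive summaries, so no treatment comparison can be biased.
- SAP 10.2 carries the dedicated TEAE definition, and AE collection stops at about 30 days anyway.

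All of this bears on size and largely stands. It is why the point should be corrected but does not threaten the trial's conclusions.

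A second argument is that misflagged events remain visible in listings. SAP 10.2 promises this: "Subject listings will also be provided for all AEs, all SAEs, all AEs leading to early discontinuation from the study". SAP 6.6 and Protocol 10.3.9 make similar commitments, and SAP 7.3.1 says listings show the recorded dates. That stands in part. However, apart from deaths, the AE listings named in SAP 14.5 are restricted to treatment-emergent events, beginning with "Part II Listing 16.2.7.3.1 Listing of Treatment Emergent Adverse Events". The promised listing of all AEs is not among them. A misflagged event may therefore appear in no named AE listing, although the display examples are in a separate attachment that could not be checked.

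A third argument is that the stated principle and the SAP 10.2 fallback show an inclusive intent. They do, but a programmer follows the explicit example, and the example does the opposite.

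**Conclusion.** The point holds. As written, SAP 7.3.1 classes an on-treatment AE as pre-treatment when only its month is known, that month is the month of first dose, and dosing did not start on the 1st. The fallback in SAP 10.2 does not clearly rescue it. Under uniform first-dose and onset dates, about two thirds of day-missing Cycle 1 onsets are affected. The share falls quickly as the onset window lengthens.

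The effect on total AE counts depends on the rate of partial dates, which is unknown and probably low. The consequence lies in the Part II safety summaries and possibly the Part 2 DLT tabulation, not in escalation decisions. The conflict between the SAP 7.2 and 10.2 windows is plain from the text. It matters by about 3 days or up to about 30, depending on how study termination is dated.

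**What to change.** 1. In SAP 7.3.1, add a rule for AE start dates. If the known part matches the month and year of first dose (or the year, when the month is also missing), impute the first-dose date, unless the end date shows that the event ended before first dose. Otherwise keep the first of the month or year.
2. State that the SAP 10.2 fallback applies when no part of the onset date is known.
3. Delete the treatment-emergent sentence in SAP 7.2 and use the SAP 10.2 definition throughout. This goes with the first change: an onset imputed to the first-dose date is inside the 10.2 window but unclear under 7.2.

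Under the new rule, misclassified day-missing onsets on Days 1 to 21 fall from 4,893 to 0 of 7,665 in the same enumeration.

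The cost is two or three sentences and a small program change. The downside is some over-counting. Of day-missing onsets on Days −28 to −1, 5,348 of 10,220 (52%) share the month of first dose and would be counted as treatment emergent when no end date shows otherwise. That is the cautious direction for a safety summary.

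As a separate small step, naming the all-AE listing in SAP 14.5 would keep any misflagged event in view.

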### 7.3.2 Non-Date Values

Every effort will be made to obtain the protocol-required data for all study assessments that are scheduled for each scheduled visit for all subjects who have been enrolled. No data imputation will be applied to missing study data except for imputing visit dates to classify AE and concomitant medication data into the study phase of "pre-treatment," "during treatment," or "post-treatment."

Page 20

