k Bone marrow aspirates will be obtained at Screening, Cycle 1-Day 22, and every other cycle thereafter. At treatment discontinuation visit, bone marrow aspirates will not be obtained if termination is due to disease progression.

\* Physical examinations should be symptom driven after the Screening Visit.

\*\* Assessments of current disease status will be obtained at Screening, Cycle 1–Day 22, and every other cycle thereafter.

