## 7.2 DISCONTINUATION OF INDIVIDUAL PATIENTS

Patients are to be withdrawn from the study for any of the following reasons:

- Withdrawal of informed consent
- Disease progression (at the discretion of the PI)
- Unacceptable toxicity
- Changes in the patient's condition which render the patient unacceptable for further treatment in the judgment of the PI
- At least 3 interruptions of BVD-523 intake of > 7 days each, or 8 consecutive days
- Patient becomes pregnant (withdrawal is required)
- Patient is lost to follow-up

Patients will also to be withdrawn at any time if the Investigator concludes that it would be in the patient's best interest for any reason. Protocol violations do not lead to patient withdrawal unless they constitute a significant risk to the patient's safety.

Patients can voluntarily withdraw from the trial for any reason at any time. They are to be considered withdrawn if they state an intention to withdraw, fail to return for visits, became lost to follow up for any reason, or if any of the following occurs:

- Discovery of patient ineligibility
- Significant errors in treatment compliance of at least three interruptions of 7 days each, any treatment interruption of ≥8 consecutive days, or incomplete dosing for greater than 7 days
- Missed / unscheduled / off-schedule / incomplete / incorrect assessments that result in patients being put at risk.

In Part 1 of the study, patients who withdraw at any time due to unrelated AEs preceding the last visit of Cycle 1 (Day 22) will constitute an early discontinuation and must be replaced in order to ensure proper data accrual for dose escalation decisions. A patient who experiences a DLT in Cycle 1 and withdraws before Day 22 either because of the toxicity or otherwise, will nonetheless have that DLT counted in the assessment of potential cohort expansion and/or dose escalation (Table 3.2).

In Part 2 of the study, patients who withdraw at any time preceding the last visit of Cycle 2 (Day 43) will constitute an early discontinuation and will not be replaced and will be evaluated in the Intent to Treat analysis. If patients withdraw due to progressive disease or AEs, replacement of such patients potentially introduces bias into the study. If a patient withdraws for other reasons, replacement of the patient will be decided by the Safety Monitoring Committee.

The investigator must determine the primary reason for a patient's withdrawal from the study and record this information on the eCRF.

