#### 10.1.2 Determination of Sample Size

The sample size for Part 1 of this study was determined by clinical rather than statistical considerations. Approximately 20 patients will be treated in Part 1 of this study (Dose Escalation) to establish dose limiting toxicities (DLT), maximum tolerated dose (MTD), and the recommended Phase 2 dose (RP2D).

After the completion of Part 1 of this study, up to 40 additional AML or MDS patients with or without RAS mutations will be treated with the RP2D of BVD-523. The purpose of the second phase of this study is to document that there is some evidence of a response. With 20 subjects in each group, there is an 88% probability of seeing at least one positive response in each group if the true response rate is at least 10%.

The observation of DLTs in more than 33% of patients in any Part 2 cohort with at least 6 patients enrolled at any time during Part 2 will trigger temporary stopping of patient enrollment and revision of the definition of the MTD and RP2D in the specific cohort. Subsequent patients will be treated with a dose lower than the initial RP2D and this dose will be determined in discussion with the Clinical Investigators, the Medical Monitor, and the Sponsor.

Up to 6 study centers are expected to enroll patients for this study.

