### 4 SAMPLE SIZE CONSIDERATIONS

The expected sample size is 60 subjects: 20 in Part 1 and 40 in Part 2 (20 subjects each in RAS mutant positive and RAS mutant negative groups). This sample size was selected based on the sample size for similar Phase 1 oncology clinical trials.

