### 5.4 PER PROTOCOL

The Per Protocol (PP) Population will consist of all subjects in the mITT population who receive at least 1 dose of study drug, complete the first protocol-specified tumor measurement evaluation (except for study drug-related AE), and complete the study without a major protocol deviation (see Section 8.6). Demographic and baseline characteristics will be tabulated for the PP population. Additionally, the PP population will be used for calculating MTDs in Part 1 and response in Part 2.

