### 9 EFFICACY ANALYSIS

Unless otherwise stated, efficacy analyses will be performed on both the modified ITT and PP populations.

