## 14.2 EFFICACY SUMMARY FIGURES AND TABLES

Table	Title	Population
Part II - Table 14.2.1.1.1	AML Disease Response by Bone Biopsy (IWG 2003)	mITT Population
Part II - Table 14.2.1.1.2	AML Disease Response by Bone Biopsy (IWG 2003)	PP Population
Part II - Table 14.2.1.2.1	MDS Disease Response by Bone Biopsy (IWG 2006)	mITT Population
Part II - Table 14.2.1.2.2	MDS Disease Response by Bone Biopsy (IWG 2006)	PP Population
Figure	Title	Population

N/A

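### The per-protocol response rate in Part 2 leaves out patients who fail before the first marrow, and it ranks equally with the mITT rate

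*SAP*

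**What the plan says.** **Timing of the marrow.** Response rests on bone marrow results (Protocol 3.5.2). The schedule in Protocol Table 6.3, repeated in SAP Table 3.1, places the first on-treatment marrow at Cycle 1 Day 22. Footnote k adds that at the discontinuation visit "bone marrow aspirates will not be obtained if termination is due to disease progression". Disease status is still to be recorded at that visit, with no exception for progression (Protocol 5.2.6).

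**PP population.** SAP 5.4 requires that the subject "complete the first protocol-specified tumor measurement evaluation (except for study drug-related AE"), along with at least one dose and no major deviation. The protocol's own PP definition (10.2.3) has no condition about a first evaluation; the SAP added it.

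**mITT population.** SAP 5.3 takes eligible consented subjects, treated or not, and names this population for Part 2 response.

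**Which population leads.** SAP 5.4 also names PP for Part 2 response. SAP 9 says "efficacy analyses will be performed on both the modified ITT and PP populations", and SAP 14.2 lists each response table twice, once per population (for example "AML Disease Response by Bone Biopsy (IWG 2003")). Neither is called primary.

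**Missing response.** SAP 7.3.2 states: "No data imputation will be applied to missing study data except for imputing visit dates to classify AE and concomitant medication data". SAP 9.2.2 lists the response categories, including one for less than partial remission, but gives no denominator and no rule for a subject never assessed. The mITT denominator sentence in SAP 8.1 concerns disposition percentages.

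**Early withdrawals.** Protocol 7.2 keeps Part 2 withdrawals before Day 43 in the Intent to Treat analysis and warns: "If patients withdraw due to progressive disease or AEs, replacement of such patients potentially introduces bias into the study".

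**The concern.** Whether a patient has a post-baseline marrow depends on the outcome. Someone who leaves for progression before Day 22 is a treatment failure, and the schedule ensures that no marrow is taken. A PP set that requires the first evaluation, and excuses only drug-related toxicity, therefore selects against early failure. The responders all stay and some non-responders go, so the bias has one direction.

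Documenting response is the stated purpose of Part 2 (Protocol 10.1.2), and response appears under the primary endpoints in Protocol 10.3.5 and SAP 9.1. With about 20 patients per RAS group, a few exclusions move the percentage visibly. Without a ranking of the two populations, the more favourable rate can be quoted as the study's result.

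**Working it through.** **1. The plan's own figure.** Inputs: 20 per group (SAP 4: "40 in Part 2 (20 subjects each in RAS mutant positive and RAS mutant negative groups")) and a true rate of 10% (Protocol 10.1.2: "there is an 88% probability of seeing at least one positive response in each group if the true response rate is at least 10" per cent).

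P(at least one response) = 1 − (1 − 0.10)^20 = 1 − 0.1216 = 0.878. This agrees with the stated 88%, for each group taken separately.

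**2. Who lacks a post-baseline marrow.** Nothing is scheduled between Screening and Day 22. A patient who leaves for progression before Day 22 has no Day 22 marrow and none at exit. A patient who dies before Day 22 has none either.

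**3. What each population does with them.**

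| Patient with no evaluation by Day 22 because of | mITT (SAP 5.3) | PP (SAP 5.4, natural reading) |
|---|---|---|
| Study drug-related AE | kept | not excluded by this condition |
| Progression | kept | excluded |
| Unrelated death | kept | excluded |

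For those kept in mITT, no sentence says that they count as non-responders.

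**4. Size.** The documents give no early-failure rate, so this step is an assumption throughout. Let x be the responders among 20 treated patients and k the early failures dropped.

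Observed rate = x/(20 − k). Inflation factor = [x/(20 − k)] ÷ [x/20] = 20/(20 − k).

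With x = 2 and exact (Clopper-Pearson) 95% intervals:

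| k | Rate | 95% CI | Factor |
|---|---|---|---|
| 0 | 2/20 = 10.0% | 1.2% to 31.7% | 1.00 |
| 2 | 2/18 = 11.1% | 1.4% to 34.7% | 1.11 |
| 4 | 2/16 = 12.5% | 1.6% to 38.3% | 1.25 |
| 6 | 2/14 = 14.3% | 1.8% to 42.8% | 1.43 |
| 8 | 2/12 = 16.7% | 2.1% to 48.4% | 1.67 |

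If the k patients stay in the denominator as non-responders, the rate is 2/20 = 10.0% for every k. The factor does not depend on x.

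**5. Effect on the 88%.** Removing non-responders changes 20 to 20 − k but leaves x as it is. Whether x is at least 1 is unchanged, so the 88% probability is unaffected.

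**The case against.** The case against is substantial and narrows the point.

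- **A reader might infer that early progressors have no response record at all.** They do have a place to be recorded. Disease status is assessed at discontinuation, and the eCRF and both SAP response tables carry a less-than-PR category. What is missing by design is the marrow; what is missing from the text is a sentence assigning these patients to that category.
- **A reader might infer that the no-imputation rule shrinks the mITT denominator.** It does not. mITT keeps these patients, and counting someone with no documented response as not having responded need not be imputation. The mITT rate would be inflated only if its percentages were based on non-missing responses, which the SAP neither states nor excludes.
- **A reader might infer that the PP rate cancels Protocol 7.2.** It does not, because the mITT tables still carry the early withdrawals. The trouble is an equal-ranking second rate with the opposite handling.
- **A reader might infer that no output by RAS group is planned.** SAP 6.2 requires Part 2 analyses separately by RAS status. Table examples sit in an attachment outside these documents, so layouts cannot be judged from titles. A table pooling AML and MDS would be a preference.
- **The PP exclusion rests on a reading.** The evaluation is described in solid-tumour terms not defined for AML or MDS, and disease status at discontinuation might arguably satisfy it. But both disease status and marrow are first scheduled on treatment at Day 22, and a patient who dies earlier may have neither. The exception written for drug-related AEs also implies that other reasons are not excused.
- **Not every early progressor leaves.** Withdrawal for progression is at the investigator's discretion and treatment beyond progression is allowed. Eligibility also requires a predicted life expectancy of at least 3 months. So k may be small, and even 16.7% lies within the interval for 2/20.
- **No formal efficacy analysis is planned.** True, but a response rate will still be reported in each population, and a stated rule biases one of them.

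**Conclusion.** The point holds in limited form. On the natural reading of SAP 5.4, patients who leave for progression or die of unrelated causes before Day 22 drop out of the PP denominator. Because PP and mITT are both used for Part 2 response with neither primary, a co-equal rate is conditioned on not failing early and is biased upward. In mITT the gap is one of wording: these patients are kept, but the text does not say that they count as non-responders.

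The size cannot be fixed from the documents. Assuming 2 responders in 20 and 2 to 8 early failures dropped, the rate is 11.1% to 16.7% against 10.0%, a factor of 1.11 to 1.67; with no early failures there is no bias. The 88% calculation stands. The SAP should be changed, but nothing here makes the mITT analysis wrong or the trial's design unsound.

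**What to change.** Before the Part 2 outputs are produced:

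- **SAP 5.4:** keep patients who progressed or died before the first evaluation in PP, as non-responders, and say what the first evaluation is for AML and MDS.
- **SAP 5.3 and 9:** name mITT as the primary response population and PP as supportive.
- **SAP 9.2.2:** state that an mITT subject with no post-baseline response assessment counts as a non-responder in the denominator. Give exact (Clopper-Pearson) 95% confidence intervals for the response proportions by RAS group, and say which listed categories count as a response.

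The cost is a few sentences and an interval added to the response output; no new data are needed. The quoted response rate may be lower, partly because SAP mITT also includes eligible subjects who were never treated.
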